## **7.2 Exclusion Criteria**

The subject must be excluded from participating in the trial if the subject:

- 1. Subjects who have a history of clinically significant endocrine, gastrointestinal (including motility disorder and intestinal obstruction), cardiovascular, hematological, hepatic, immunological, renal, respiratory, genitourinary, or major neurological (including stroke and chronic seizures) abnormalities or diseases will be excluded from the trial.
- 2. Has participated in another investigational trial within 4 weeks before the pretrial visit (Screening). The 4-week window will be derived from the date of the last trial procedure and/or AE related to the trial procedure in the previous trial to the pretrial/Screening Visit of the current trial.
- 3. Is an employee or immediate family member (eg, spouse, parent, child, sibling) of the sponsor.
- 4. Has a history of cancer (malignancy).
- 5. Has a history of significant multiple and/or severe allergies (eg, food, drug, latex allergy) or has had an anaphylactic reaction or significant intolerance to prescription or nonprescription drugs or food.
- 6. Has a positive alcohol or drug screen.
- 7. Is a lactating/nursing woman.
- 8. Had major surgery, donated or lost 1 unit of blood (approximately 500 mL) within 8 weeks of the first dose of study drug.
- 9. Has a known hypersensitivity to any component of the formulation of TAK-906 or related compounds, or to itraconazole (see Product Insert).
- 10. Is unable to refrain from or anticipates the use of any medication, including prescription and nonprescription drugs or herbal remedies, beginning approximately 7 days before administration of the initial dose of trial drug, throughout the trial (including washout intervals between trial periods), until the Follow-up Visit. There may be certain medications that are permitted, see Section [7.3](#).

11. Has a history of alcohol consumption exceeding 2 standard drinks per day on average (1 glass is approximately equivalent to: beer [354 mL/12 ounces], wine [118 mL/4 ounces], or distilled spirits [29.5 mL/1 ounce] per day).
12. Consumes excessive amounts, defined as greater than 6 servings (1 serving is approximately equivalent to 120 mg of caffeine) of coffee, tea, cola, energy drinks, or other caffeinated beverages per day.
13. Has a substance abuse disorder.

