## **7.0 SELECTION AND DISCONTINUATION/WITHDRAWAL OF SUBJECTS**

### **7.1 Inclusion Criteria**

In order to be eligible for participation in this trial, the subject must:

1. Understand the trial procedures and agree to participate by providing written informed consent.
2. Be willing and able to comply with all trial procedures and restrictions.
3. Be a man or woman (with no child bearing potential) aged 18 to 55 years, inclusive, at the Screening Visit.
4. Have a body mass index (BMI)  $\geq 18$  and  $\leq 30 \text{ kg/m}^2$  and a body weight  $>50 \text{ kg}$  at the Screening Visit.
5. Be a nonsmoker who has not used tobacco- or nicotine-containing products (eg, nicotine patch) for at least 6 months before administration of the initial dose of trial drug/invasive procedure.
6. Be judged to be in good health by the investigator, based on clinical evaluations including laboratory safety tests, medical history, physical examination, 12-lead ECG, and vital sign measurements performed at the Screening Visit and before administration of the initial dose of trial drug.
7. Meet the following birth control requirements:
  - Is a male subject\* who is sterile or agrees to use an appropriate method of contraception, including a condom with spermicide, from trial drug administration on the first day of the first dose until 5 half-lives plus 90 days after administration of the last dose of trial drug. No restrictions are required for a vasectomized male subject provided the subject is at least 1 year post-bilateral vasectomy procedure before trial drug administration on the first day of the first dose. A male subject whose vasectomy procedure was performed less than 1 year before trial drug administration on the first day of the first dose must follow the same restrictions as a nonvasectomized man. Appropriate documentation of surgical procedure should be provided.
  - Is a male subject who agrees to not donate sperm from trial drug administration on the first day of the first dose until 5 half-lives plus 90 days after administration of the last dose of trial drug.
  - Is a female subject\* with no childbearing potential, defined by at least 1 of the following criteria:

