**Table 7.a Excluded Medications, Supplements, and Dietary Products**

Category	Between Screening and Enrollment (Days -28 to Predose [Day 1])	Randomization Post-Enrollment (Day 1) to Follow-up
Tobacco- and nicotine-containing products	Completely restricted	Completely restricted
Cannabis products	Completely restricted	

• Completely restricted

Alcohol	Completely restricted 7 days before dosing	

• Completely restricted 7 days before dosing

• At all other times no more than 3 units/day

Xanthine and/or caffeine	Completely restricted 48 hours before dosing	
Completely restricted 48 hours before dosing
 
At all other times no more than 6 units/day

Medications	Completely restricted 7 days before dosing	Completely restricted (a)
Food substance		
• Grapefruit /grapefruit juice	Completely restricted 7 days before dosing	Completely restricted
• Fruit	No restriction	No restriction
• Fruit juice	No restriction	Dosing will occur without consumption of fruit juice. Fruit juice is restricted 4 hours after dosing.
• Mustard green (b)	Completely restricted 7 days before dosing	Completely restricted
• Charbroiled meat	Completely restricted 7 days before dosing	Completely restricted

(a) If medications are required to treat an AE, certain medications may be allowed after discussion and agreement between the sponsor and principal investigator.

(b) Mustard green family includes kale, broccoli, watercress, collard greens, kohlrabi, Brussel sprouts, and mustard.

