**Urine Drug Screen**

A urine drug screen will include the following tests:

Amphetamines	3,4-methylenedioxy-methamphetamine
Barbiturates	Methadone/metabolite
Benzodiazepines	Opiates
Buprenorphine/metabolite	Oxycodone/oxymorphone
Cannabinoids	Phencyclidine
Cocaine/metabolites	Cotinine

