## 7.6 Medication History and Concomitant Medications

Medication history information includes any medication stopped at or within 28 days prior to signing of informed consent. Medications used from signing of informed consent through the end of study will be considered as concomitant medications.

Medication history and concomitant medications will be coded using the WHO Drug, and will be presented in the data listing. There will be no summary or inferential analysis of medication history and concomitant medications.

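### One 7-day medication window covers CYP3A4 inducers and inhibitors too; residual enzyme effects could distort the reference exposure more than the itraconazole exposure

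*Protocol*

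**What the plan says.** Exclusion 10 in Protocol 7.2 concerns "any medication, including prescription and nonprescription drugs or herbal remedies, beginning approximately 7 days before administration of the initial dose of trial drug". The Medications row of Table 7.a gives the same pre-enrolment rule: "Completely restricted 7 days before dosing". Neither place distinguishes agents that act on drug-metabolising enzymes, although Protocol 4.2 names CYP2C8, 3A4 and 1A2 as possibly involved and the primary objective is the effect of CYP3A4 inhibition.

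Other rules remove part of the field:

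- Exclusion 6 ("Has a positive alcohol or drug screen") applies to a urine panel that includes "Barbiturates".
- Table 7.a bars cannabis completely from Screening.
- Exclusion 2 bars participation in another investigational trial within 4 weeks before Screening.
- Inclusion 6 and exclusions 1 and 4 require good health and rule out a history of clinically significant disease or cancer.
- Inclusion 5 requires a nonsmoker who "has not used tobacco- or nicotine-containing products (eg, nicotine patch) for at least 6 months".

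SAP 7.6 records earlier use: "Medication history information includes any medication stopped at or within 28 days prior to signing of informed consent". Everything taken from consent onward counts as concomitant. Both are listed only, with no summary or inferential analysis.

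**The concern.** Enzyme induction fades with enzyme turnover after the inducer has gone, and some inhibition may also outlast the last intake. Seven days without the agent need not mean baseline activity.

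The order of treatment is fixed. The reference dose (TAK-906 alone, Period 1 Day 1) is the one nearer to the last permitted intake. The test dose (Period 2 Day 4) is further away, and itraconazole is also suppressing CYP3A4 by then. A residual effect therefore does not cancel within the subject, and there is no second sequence in which the error would fall on the other treatment.

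Nothing later in the plan picks this up. The case-by-case PK decisions in Protocol 11.1.1.2 and SAP 7.2 cover noncompliance with dosing and incomplete data. A subject who kept to the 7-day rule is neither. At stake is a possible bias in the primary ratios for Cmax and AUC.

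**Working it through.** The plan gives no figure for this effect, so there is none to reproduce. Its 80% power statement does not enter the argument.

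**Timing, from the documents.** Last permitted intake to reference dose: about 7 days. Reference dose to test dose: 4-day minimum washout plus 3 days (Period 2 Day 1 to Day 4) = at least 7 days. Last intake to test dose: at least about 7 + 7 = 14 days.

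**Assumptions, not in the documents.** Three-fold induction at last intake, first-order decay with enzyme half-life h, and TAK-906 cleared wholly by CYP3A4.

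Relative clearance t days after last intake: C(t) = 1 + (3 − 1) × 2^(−t/h). If clearance is wholly by CYP3A4, itraconazole scales induced and uninduced activity by the same factor. The subject's ratio (with itraconazole over alone) is then multiplied by C(7)/C(14). One such subject in 12 multiplies the geometric mean ratio by [C(7)/C(14)]^(1/12).

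| h (days) | C(7) | C(14) | Subject's ratio × | Geometric mean ratio × (1 of 12) |
|---|---|---|---|---|
| 1 | 1.016 | 1.000 | 1.016 | 1.001 |
| 2 | 1.177 | 1.016 | 1.16 | 1.012 |
| 3 | 1.397 | 1.079 | 1.29 | 1.022 |
| 4 | 1.595 | 1.177 | 1.36 | 1.026 |

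**A wider check, also on assumptions.** Let a fraction f of clearance be by CYP3A4, and let itraconazole leave 10% of its activity. Reference AUC is proportional to 1/(f·E7 + 1 − f) and test AUC to 1/(f·0.1·E14 + 1 − f). E is residual enzyme activity relative to baseline, at 7 or 14 days. Results for f = 60% and h = 1.5, 3 and 6 days:

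- Four-fold induction: reference AUC × 0.93, 0.74, 0.56; test AUC × 1.00, 0.99, 0.93; subject's ratio × 1.07, 1.34, 1.67.
- Inhibition to 20% of activity: reference AUC × 1.02, 1.11, 1.27; test AUC × 1.00, 1.00, 1.02; subject's ratio × 0.98, 0.91, 0.80.

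With f also set to 30% and 90%, and with 2-fold induction and inhibition to 50% added, the reference was distorted more than the test in every case. Over that whole grid, one affected subject in 12 moves the geometric mean ratio by at most about +5% (induction) or −2.5% (inhibition). Two in 12 move it by at most about +9% or −5%.

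**Scale for comparison.** With the plan's n = 12 and intrasubject CV of 25%, the log-scale SD is √ln(1 + 0.25²) = 0.246 and the SE is 0.246 × √(2/12) = 0.10. The 90% CI half-width is 1.796 × 0.10 = 0.18, or about 20%.

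**The case against.** The case against has four parts.

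**Size.** A shift of 1 to 3% is far inside a confidence interval of about ±20% and an acceptance range of 50% to 200%. Induction also raises the ratio, which is conservative for a claim that exposure does not more than double. This stands, and it keeps the point modest. Residual inhibition works in the unfavourable direction, though by no more than about 2.5% for one subject in 12 in the cases tried.

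**Coverage.** A reader might infer that the criteria admit any inducer or inhibitor and that the reference will be distorted. The documents do not support that. The drug screen, the cannabis and investigational-trial rules and the health criteria remove some agents and many reasons for chronic use. Harm needs a subject who stopped a remaining agent near the limit and an effect that outlasts 7 days. The documents give neither a prevalence nor a turnover figure.

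**Reference only.** It is tempting to say that only the reference is affected and to carry its clearance change (1.18 to 1.59 for half-lives of 2 to 4 days) straight into the ratio. If clearance is wholly by CYP3A4, the inhibitor masks nothing and the test dose still carries 1.016 to 1.177. The overstatement is then 16 to 36%. Masking needs other clearance routes, and those shrink the reference distortion too (1.09 to 1.30 if CYP3A4 carries half).

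**Tobacco.** The 6-month tobacco rule might be read as showing that the plan is strict on CYP1A2 and lax on CYP3A4. Appendix A ties only the added cotinine test to CYP1A2 and gives no such reason for the 6 months. Table 7.a gives grapefruit, mustard greens and charbroiled meat the same 7 days before dosing.

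None of this supplies a reason for using 7 days for enzyme-active agents. Listing the history makes an affected subject visible but commits the plan to nothing.

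**Conclusion.** The point holds as a modest, conditional weakness. There is one window of about 7 days, no rule specific to enzyme-active agents, and a fixed order that puts the reference dose nearer to the last permitted intake. A residual effect could therefore distort the reference more than the test, inflating the ratio under induction and diluting it under inhibition.

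With 3-fold induction, half-lives of 2 to 4 days, clearance wholly by CYP3A4 and the minimum interval between doses, the overstatement is about 16 to 36% for that subject and 1.2 to 2.6% in the geometric mean ratio if one of 12 is affected. At a 1-day half-life it is about 1.6% and 0.1%. The pharmacological inputs are assumptions; the dose timing is the protocol's.

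The documents do not show that such a subject will be enrolled, or that the trial's conclusion would change. The change is still worth making, because it is cheap and more subjects under the same rule would not remove the bias.

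**What to change.** - **Exclusion 10 and the Medications row of Table 7.a:** keep 7 days for medicines in general. Add a separate, longer window for known inducers or inhibitors of CYP3A4, CYP2C8 or CYP1A2, including herbal products. The sponsor should set its length and justify it, since the documents hold no turnover figure from which to derive one. The history already collected under SAP 7.6, back to 28 days before consent, would support a window of up to that length without new data collection.
- **SAP 7.9.1:** add a sensitivity analysis of the Cmax, AUClast and AUC∞ ratios without subjects whose recorded history shows recent use of such agents. Fix the list of agents and the look-back period in advance.

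The cost is one line in two places of the protocol, one extra analysis, and an occasional extra screen failure or later dosing date.

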### **7.3 Excluded Medications, Supplements, Dietary Products**

Use of excluded agents (prescription or nonprescription) or dietary products is outlined in [Table 7.a.](#)

**Table 7.a Excluded Medications, Supplements, and Dietary Products**

Category	Between Screening and Enrollment (Days -28 to Predose [Day 1])	Randomization Post-Enrollment (Day 1) to Follow-up
Tobacco- and nicotine-containing products	Completely restricted	Completely restricted
Cannabis products	Completely restricted	

• Completely restricted

Alcohol	Completely restricted 7 days before dosing	

• Completely restricted 7 days before dosing

• At all other times no more than 3 units/day

Xanthine and/or caffeine	Completely restricted 48 hours before dosing	
Completely restricted 48 hours before dosing
 
At all other times no more than 6 units/day

Medications	Completely restricted 7 days before dosing	Completely restricted (a)
Food substance		
• Grapefruit /grapefruit juice	Completely restricted 7 days before dosing	Completely restricted
• Fruit	No restriction	No restriction
• Fruit juice	No restriction	Dosing will occur without consumption of fruit juice. Fruit juice is restricted 4 hours after dosing.
• Mustard green (b)	Completely restricted 7 days before dosing	Completely restricted
• Charbroiled meat	Completely restricted 7 days before dosing	Completely restricted

(a) If medications are required to treat an AE, certain medications may be allowed after discussion and agreement between the sponsor and principal investigator.

(b) Mustard green family includes kale, broccoli, watercress, collard greens, kohlrabi, Brussel sprouts, and mustard.

### **7.4 Diet, Fluid, Activity**

#### **7.4.1 Diet and Fluid**

Subjects must abstain from all food and drink (except water) at least 8 hours before any clinical laboratory evaluations. In addition, both doses of TAK-906 will be administered after an overnight fast of at least 8 hours as food reduces its bioavailability by approximately 40%.

The bioavailability of itraconazole when administered as a PO solution is increased under fasted compared with fed conditions; therefore, itraconazole will be administered as fasted on Day 4 of

Period 2. A moderate-fat breakfast or snack may be administered on itraconazole-only days to alleviate gastrointestinal irritation. Itraconazole will be administered to subjects under clinic supervision on an outpatient basis on the morning of Days 1 to 3 of Period 2.

During confinement (optional), lunch will be provided approximately 4 hours after TAK-906 maleate dosing or 5 hours after itraconazole dosing, as applicable, on all days. Dinner will be provided approximately 9 or 10 hours after TAK-906 maleate or itraconazole dosing, respectively, on all days. An evening snack will also be permitted. The caloric content and composition of meals will be the same in each trial period. After the 24-hour postdose (Day 2 of Trial Period 1 and Day 5 of Trial Period 2) procedures have been completed, subsequent meals and snacks will be unrestricted in caloric content, composition, and timing.

#### **7.4.2 Activity**

Subjects will avoid unaccustomed strenuous physical activity (eg, weight lifting, running, bicycling) from the Screening Visit until the Follow-up visit.

#### **7.5 Criteria for Discontinuation or Withdrawal of a Subject**

1. The subject experiences an AE that requires early termination because continued participation imposes an unacceptable risk to the subject's health or the subject is unwilling to continue because of the AE.
2. Liver function test (LFT) abnormalities

In multidose studies, trial drug should be discontinued immediately with appropriate clinical follow-up (including repeat laboratory tests, until a subject's laboratory profile has returned to normal/baseline status, see Section 10.2.9.4), if the following circumstances occur at any time during trial drug treatment:

- Alanine aminotransferase (ALT) or aspartate aminotransferase (AST)  $>8$  times the upper limit of normal (ULN), or
- ALT or AST  $>5\times$ ULN and persists for more than 2 weeks, or
- ALT or AST  $>3\times$ ULN in conjunction with elevated total bilirubin  $>2\times$ ULN or international normalized ratio  $>1.5$ , or
- ALT or AST  $>3\times$ ULN with appearance of fatigue, nausea, vomiting, right upper quadrant pain or tenderness, fever, rash, and/or eosinophilia ( $>5\%$ ).

3. Significant protocol deviation. The discovery that the subject failed to meet protocol entry criteria or did not adhere to protocol requirements, and continued participation poses an unacceptable risk to the subject's health.
4. Lost to follow-up. The subject did not return to the clinic, and attempts to contact the subject were unsuccessful. Attempts to contact the subject must be documented in the subject's source documentation.

5. Voluntary withdrawal. The subject (or subject's legally acceptable representative) wishes to withdraw from the trial. The reason for withdrawal, if provided, should be recorded in the electronic case report form (eCRF).

Note: All attempts should be made to determine the underlying reason for the withdrawal and, where possible, the primary underlying reason should be recorded (ie, withdrawal because of an AE should not be recorded in the "voluntary withdrawal" category).

6. Trial termination. The sponsor, IRB, or regulatory agency terminates the trial.

## **7.6 Procedures for Discontinuation or Withdrawal of a Subject**

The investigator may discontinue a subject's trial participation at any time during the trial when the subject meets the trial termination criteria described in Section 7.5. In addition, a subject may discontinue his or her participation without giving a reason at any time during the trial. Should a subject's participation be discontinued, the primary criterion for termination must be recorded by the investigator. In addition, efforts should be made to perform all procedures scheduled for the Early Termination Visit.

## **7.7 Subject Replacement**

If a subject discontinues from the trial, a replacement subject may be enrolled, if deemed appropriate by the investigator and sponsor. The trial site should contact the sponsor for the replacement subject's treatment assignment and allocation number.

## **8.0 CLINICAL TRIAL MATERIAL MANAGEMENT**

### **8.1 Clinical Trial Drug**

Details regarding the composition and extemporaneous preparation of the active ingredient are found in the Pharmacy Manual, Compounding Instructions, and/or similar documents. Clinical trial drug will be packaged to support enrollment and replacement subjects as required. When a replacement subject is required, the sponsor needs to be contacted before dosing.

Itraconazole will be supplied by the trial site.

#### **8.1.1 Clinical Trial Drug Labeling**

Clinical trial drug packaging will be affixed with a clinical label in accordance with regulatory requirements.

#### **8.1.2 Clinical Trial Drug Inventory and Storage**

Clinical trial drug must be stored in a secure, limited-access location under the storage conditions specified on the label. Inventory (receipt and dispensing) of trial drug must be recorded by an authorized person at the trial site.

#### **8.1.3 Clinical Trial Drug Blinding**

This is an open-label trial; therefore, the sponsor, investigator, and subject will know the treatment administered.

#### **8.1.4 Accountability and Destruction of Sponsor-Supplied Drugs**

The investigator is responsible for keeping accurate records of the clinical trial drug received from the sponsor or designee, the amount dispensed to and returned by the subjects, and the amount remaining at the conclusion of the trial. For all trial sites, the local country sponsor personnel or designee will provide appropriate documentation that must be completed for clinical trial drug accountability, return, and destruction.

#### **8.1.5 Ancillary Supplies**

All ancillary supplies will be provided by either the site or Takeda, based upon availability. If provided by Takeda, unused ancillary supplies will be accounted for and disposed of as directed by Takeda or a Takeda designee.

## **9.0 TRIAL PROCEDURES**

The following sections describe the trial procedures and data to be collected as indicated in the Schedule of Trial Procedures (Section 3.0). For each procedure, subjects are to be assessed by the same investigator or site personnel whenever possible. Please note that it may become necessary to perform the following procedures at unscheduled time periods, per the discretion of the investigator. For information regarding procedures that are scheduled concurrently, see Section 6.2.3.

